#### Clinical pharmacology

In postmenopausal women with advanced breast cancer letrozole suppressed plasma levels of oestradiol, oestrone and oestrone sulphate by 75-95% of baseline in a dose dependent manner with 0.5mg and higher suppressing oestrogen oestrone and oestrone sulphate below the limits of detection. There is no detectable effect of letrozole on adrenal corticosteroid synthesis, aldosterone synthesis or androgen levels in healthy postmenopausal volunteers.

Letrozole is rapidly and completely absorbed from the gastrointestinal tract (mean absolute bioavailability of 99.9%). Food slightly decreases the rate of absorption (median  $t_{max}$ : 1 hour fasted versus 2 hours fed; and mean  $C_{max}$ : 129 $\pm$  20.3nmol/l fasted versus 98.7 $\pm$  18.6nmol/l fed) but the extent of absorption (AUC) is not changed. The minor effect on the absorption rate is not considered to be of clinical relevance and therefore letrozole may be taken without regard to meal times. Clearance is via conversion to an inactive hydroxymetabolite. Elimination is almost exclusively via the kidneys as the inactive metabolite, clearance is however not dependent on renal function.

#### Letrozole in advanced breast cancer treatment

Early phase experience with letrozole has been reproduced in large Phase III trials where the drug was generally well-tolerated, with the most frequently reported adverse events being bone pain, hot flushes, back pain, nausea and arthralgia. These were similar in both first-line and second-line settings. In the neoadjuvant setting letrozole is well-tolerated and safe, with hot flushes, arthralgia and nausea the most frequently reported adverse events. In the adjuvant context, letrozole has been compared to placebo after prior tamoxifen exposure. Here hot flushes and musculoskeletal complaints were more common with letrozole. Vaginal bleeding was less common. In addition osteoporosis was more common with letrozole and fractures were numerically, but non-significantly, more common.

Letrozole (2.5mg/day) was compared to tamoxifen (20mg/day) in a large Phase III trial in women with locally advanced or metastatic breast cancer. In this study of 907 patients, letrozole was associated with a superior median time to progression of 9.4 months versus 6.0 months,  $p < 0.0001$ . Overall response was 32% versus 21%,  $p = 0.0002$ . Letrozole (2.5 mg/day) has also been compared with megestrol acetate in women with advanced breast cancer failing prior tamoxifen. In this trial letrozole was the more active agent, with a response rate of 23.6%

versus 16.4%,  $p=0.04$ . Here letrozole, at the lower dose of 0.5mg/day, was also less active than the 2.5mg cohort.

### **Letrozole as adjuvant therapy**

Letrozole has also been studied in the adjuvant context. A large trial comparing tamoxifen for 5 years with letrozole for 5 years and two sequential arms in which the two drugs are administered in sequence, switching after 2.5 years to the alternative agent, has been conducted and preliminary data are expected shortly. Letrozole has also been compared with placebo after the completion of 5 years adjuvant therapy. In this study of 5187 women an improvement in disease-free survival emerged after a median follow-up of 2.4 years when the study was unblinded. The Hazard Ratio (HR) was 0.58, with an estimated 4 year disease free survival of 93% versus 87%. Preliminary data from a complex adjuvant letrozole trial, BIG 1-98, has also been released. This large randomised study compares tamoxifen for 5 years with letrozole for 5 years and sequential tamoxifen/letrozole and letrozole/tamoxifen. Data from all four arms has been analysed to provide a comparison of tamoxifen versus letrozole, with patient data censored at the crossover point within the switching arms. This shows superiority for letrozole versus tamoxifen, HR 0.81 (95% CI 0.7-0-0.93). While generally well-tolerated this trial has reported a non-significant excess of fatal myocardial infarctions in the letrozole treated group (13 versus 6 in over 8000 patients). As it is non-significant and was not seen in the MA-17 trial the importance and potential cause is speculative and unlikely to be relevant to a short-term 16 week exposure to letrozole (Thurliman et al. ASCO 2005).

### **Neoadjuvant tolerability**

The clinical efficacy of neoadjuvant letrozole was discussed earlier; letrozole is well-tolerated with serious adverse events only rarely encountered (one pulmonary embolus reported in the P024 study). Adverse events occurring in  $>2\%$  of patients are reproduced from this study in Table 1.

**TABLE 1: Adverse Events with neoadjuvant letrozole and tamoxifen**

ADVERSE EVENTS	Letrozole, n= 157	Tamoxifen, n=170
Hot Flushes	20%	24%
Nausea	5%	5%
Asthenia	2%	3%
Fatigue	3%	2%
Increased sweating	2%	3%
Weight gain	2%	2%
Leukorrhea	0%	4%
Pruritis	1%	2%
Headache	3%	1%
Dyspepsia	1%	2%
Hair Thinning	2%	1%

### 3.6.2 Exemestane

Exemestane is a very potent, orally active, selective and long lasting steroid, irreversible inactivator of aromatase. In *in vitro* studies exemestane appeared to be 2.8 and 156 times more potent than the steroid formestane and the non-steroidal aminoglutethimide (AG), respectively, in inhibiting human placental aromatase.

*In vivo* studies of aromatase inactivation indicate that exemestane, by the oral route, is several times more potent than formestane and suppresses plasma oestrogen by approximately 98% compared with baseline. Exemestane has no noteworthy binding to oestrogen, progesterone, glucocorticoid or mineralocorticoid receptors and only a very low binding to the androgen receptor (Relative Binding Affinity, RBA, 0.2% from that of dihydrotestosterone, DHT). However, its metabolite FCE 25071 (17-hydro-exemestane) was found to have a binding affinity to the androgen receptor (100-fold higher than that of exemestane (RBA 27% from and 0.28% that of DHT, respectively) (Pfizer Inc, data on file).

#### **Exemestane in the treatment of advanced breast cancer**

Exemestane (25mg/day) has been compared to tamoxifen (20mg/day) in first-line therapy for advanced breast cancer in the EORTC 10951 randomised Phase III study. Preliminary data shows a significant response rate advantage to exemestane (46% versus 31%,  $p=0.005$ ). Time to progression was also longer, 10 months versus 6 months. This was not significant in the primary analysis using a log rank test,  $p=0.121$ , but was significant with a secondary Wilcoxon sensitivity analysis,  $p=0.028$ . Exemestane was well-tolerated with hot flushes, bone pain and gastrointestinal adverse events the most commonly reported events.

Exemestane (25mg daily) was evaluated in a Phase III, randomised double-blind, comparative study of postmenopausal women with advanced breast cancer who had disease progression after hormonal treatment with anti-oestrogens (primarily tamoxifen) for metastatic disease or as adjuvant therapy. In this study, 769 patients were randomised to receive exemestane 25mg once daily ( $n=366$ ) or megestrol acetate 40mg four times daily ( $n=403$ ). Response rate for exemestane was 15.0% versus 12.4% for megestrol acetate. Time to progression was longer with exemestane (20.3 weeks versus 16.6 weeks,  $p=0.037$ ) and survival was superior, median survival for exemestane was not reached versus 123 weeks for megestrol acetate,  $p=0.039$ .

#### **Exemestane as adjuvant therapy**

The Intergroup Exemestane Study (IES) randomised women with early breast cancer who were disease free after 2-3 years of prior tamoxifen therapy to either continue to complete 5 years of adjuvant tamoxifen or to commence exemestane (25mg) once daily. This double-blind study of over 4,700 patients has recently published interim findings after a median follow-up of 30 months. This study, in a different population, has shown a somewhat larger difference than the ATAC study with a HR of 0.68. This translates to an absolute advantage of 4.77% at 36 months. Within the receptor positive subgroup the hazard ratio rises to 0.64 (95% CI 0.52-0.79).

In this study exemestane was well-tolerated, with arthralgia and hot flushes again the commonest reported adverse events, but diarrhoea was also seen here. Osteoporosis was more commonly reported with letrozole and fractures were numerically but not significantly more common (Table 2).

The TEAM trial is a large multinational study initially designed to compare 5 years of exemestane with 5 years of tamoxifen. This trial has been revised in the light of the IES data to

compare exemestane as initial therapy versus a switching policy in which women initiated on tamoxifen cross over to exemestane after 2-3 years.

### Exemestane tolerability

Exemestane has been reported as well-tolerated in the small neoadjuvant studies described but a detailed breakdown of the adverse events has not been reported. Table 2 summarises data from the IES trial, which has provided the most detailed comparative information on the tolerability of exemestane and tamoxifen. The most significant toxicities that are worse with exemestane are joint pains and diarrhoea. The TEAM study has also reported short-term tolerability data in the adjuvant setting which demonstrates predominantly better tolerability with exemestane.

**TABLE 2: Adverse events in the IES trial significantly different, or different by >1% or common (>5%)**

ADVERSE EVENTS (ANY GRADE)	Exemestane % (n = 2309)	Tamoxifen % (n = 2332)	P value
Arthralgia	5.4	3.6	0.01
Diarrhoea	4.3	2.3	0.001
Throboembolic AEs	1.0	2.0	0.01
Thromboembolic SAEs	1.3	2.4	0.005
Vaginal bleeding	4.0	5.6	0.01
Other gynaecological symptoms	5.8	9.0	<0.001
Endometrial cancer	0.21 (5 events)	0.46 (11 events)	Not stated
Other malignancy	22	42	Not stated
Cramp	2.8	4.4	0.0007
Sweating	18.6	18.1	
Headache	18.6	16.4	0.09
Dizziness	12.5	12.1	0.93
Visual disturbance	7.4	5.8	0.04
Depression	5.2	4.0	
Osteoporosis	7.4	5.7	0.05
Clinical fracture	3.1	2.3	0.08

## 4. STUDY RATIONALE / TREATMENT SELECTION

The hypotheses to be addressed in this bifactoral Phase III trial are that exemestane may be superior to letrozole (arguably the present standard of care), as primary neoadjuvant endocrine therapy for early stage ER positive breast cancer in postmenopausal women, and that the activity of aromatase inhibitors in this setting may significantly be enhanced by the addition of the selective COX 2 inhibitor, celecoxib.

The rationale for the comparison of letrozole and exemestane is the ostensibly greater response rate reported for exemestane in randomised Phase II studies of exemestane versus tamoxifen than for letrozole in Phase III studies versus tamoxifen. Further justification for the formal comparison refers to their different mechanisms of action. Lastly, the Investigators feel that further exploration of their clinical activity of neoadjuvant endocrine therapy in this population is long overdue and has the potential to impact on clinical practice, notwithstanding the benefits of breast cancer screening.

The conventional tool for the development of new systemic therapies is presently the randomised Phase III clinical trial. Conventionally, in the adjuvant setting this endeavour requires 2-3000 patients and may take 10 years from inception, funding, launch, execution, follow-up and

analysis. By contrast, randomised trials of systemic therapy in the primary or neoadjuvant setting offer economies of scale and the opportunity for time-scale compression. Over recent years compelling evidence has accumulated to link various measures of primary tumour response to eventual disease-free survival, thus validating their candidacy as surrogate endpoints. Two recent trials demonstrated that primary hypotheses tested in the neoadjuvant setting have the power to answer therapeutic questions with a relatively small number of patients because the biological predictors of response are likely to be strong.

## 5. TRIAL DESIGN / OBJECTIVES AND OUTCOME MEASURES

### TRIAL OBJECTIVES

To determine if exemestane is superior to letrozole as primary neoadjuvant endocrine therapy for early stage ER positive breast cancer in postmenopausal women, and whether the activity of aromatase inhibitors in this setting may be enhanced by the addition of the selective COX 2 inhibitor celecoxib.

### TRIAL DESIGN

Prospective Phase III, multicentre, bifactorial (four-arm), randomised clinical trial, with both open label and placebo-controlled comparisons.

### OUTCOME MEASURES

#### Primary

- Objective clinical response (Complete Response, Partial Response) to neoadjuvant treatment

#### Secondary

- Objective ultrasound-determined response (CR, PR) to neoadjuvant treatment
- Type of surgery
- Axillary lymph node involvement at surgery
- Complete pathological response
- Local recurrence-free survival
- Progression-free survival
- Overall survival

#### Translational sub-study

- Biological profiling for prognostic and predictive indicators

## 6. PATIENT SELECTION

### 6.1 Inclusion criteria

The study population consists of postmenopausal women diagnosed with resectable breast cancer, who meet the following eligibility criteria:

- Biopsy proven, ER positive invasive breast cancer (where ER positive is defined as equivalent to an ER “Quick or Allred score” of 3 or greater)
- Tumour, measured on U/S, as greater than 2 cm in diameter
- Postmenopausal, defined as:
  - Any Age:- bilateral surgical oophorectomy
    - amenorrhea  $\geq$  5 years (any cause)

Age  $\geq$  50 yrs:- natural amenorrhea for  $\geq$  1 year

Age  $<50$  yrs: - if amenorrhea  $< 5$  years or hysterectomy without bilateral surgical oophorectomy, then FSH, LH and oestradiol must be assayed to confirm postmenopausal status

- Adequate haematological, renal and liver function, defined as a platelets of  $>100 \times 10^9/l$ , white blood cell count of  $>3 \times 10^9/l$ , creatinine  $<110$  mmol/l, AST and/or ALT  $< 1.25 \times$  upper limit of normal
- Patients must be fit to complete surgery for their breast cancer
- Written informed consent
- ECOG performance status 0,1 or 2

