### MAIN SELECTION CRITERIA

Women with a histological diagnosis of early invasive breast carcinoma, meeting the following criteria:

- Postmenopausal
- ER positive
- Breast tumour >2cm by clinical evaluation
- No previous treatment for breast cancer
- Adequate haematological, renal and hepatic function
- ECOG performance status 0, 1 or 2

[figure not shown]

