### At Screening

- Relevant medical history including:
  - cardiac history
  - thromboembolic history
  - rheumatological history
  - other serious acute or chronic conditions
- Concomitant medication (description of other medication prescribed for more than 7 days and taken within one month of randomisation)
- ECOG performance status (Appendix 1)
- Clinical examination, including height and body weight
- Uni-dimensional tumour measurement by calipers of the greatest dimension
- Tumour assessment by ultrasound
- Base-line blood tests: full blood count; urea + creatinine + electrolytes; liver function tests
- Blood pressure measurement
- NYHA classification (see section 6.2)

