#### **Primary Outcome Measure**

- Objective clinical response (CR, PR) to neoadjuvant treatment

Objective clinical response as measured by callipers is defined as either a partial or complete response. A complete clinical response (CR) is defined as no palpable lesion from which to take calliper measurements. A partial clinical response (PR) is defined as a decrease in the greatest uni-dimensional measurement by callipers of at least 30%.

Patients who achieve a CR or a PR will be defined as achieving an objective clinical response to neoadjuvant treatment.

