## Appendix 4: RECIST Criteria

### Response Evaluation Criteria In Solid Tumours (RECIST) Quick Reference:

#### ELIGIBILITY

Only patients with measurable disease at baseline should be included in protocols where objective tumor response is the primary endpoint.

**Measurable disease:** the presence of at least one measurable lesion. If the measurable disease is restricted to a solitary lesion, its neoplastic nature should be confirmed by cytology/histology.

**Measurable lesions:** lesions that can be accurately measured in at least one dimension with longest diameter  $\geq 20$  mm using conventional techniques or  $\geq 10$  mm with spiral CT scan.

**Non-measurable lesions:** all other lesions, including small lesions (longest diameter  $<20$  mm with conventional techniques or  $<10$  mm with spiral CT scan), i.e., bone lesions, leptomeningeal disease, ascites, pleural/pericardial effusion, inflammatory breast disease, lymphangitis cutis/pulmonis, cystic lesions, and also abdominal masses that are not confirmed and followed by imaging techniques; and:

- All measurements should be taken and recorded in metric notation, using a ruler or calipers. All baseline evaluations should be performed as closely as possible to the beginning of treatment and never more than 4 weeks before the beginning of the treatment.
- The same method of assessment and the same technique should be used to characterize each identified and reported lesion at baseline and during follow-up.
- Clinical lesions will only be considered measurable when they are superficial (e.g., skin nodules and palpable lymph nodes). For the case of skin lesions, documentation by color photography, including a ruler to estimate the size of the lesion, is recommended.

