#### Methods of Measurement

- CT and MRI are the best currently available and reproducible methods to measure target lesions selected for response assessment. Conventional CT and MRI should be performed with cuts of 10 mm or less in slice thickness contiguously. Spiral CT should be performed using a 5 mm contiguous reconstruction algorithm. This applies to tumours of the chest, abdomen and pelvis. Head and neck tumours and those of extremities usually require specific protocols.
- Lesions on chest X-ray are acceptable as measurable lesions when they are clearly defined and surrounded by aerated lung. However, CT is preferable.
- When the primary endpoint of the study is objective response evaluation, ultrasound (US) should not be used to measure tumour lesions. It is, however, a possible alternative to clinical measurements of superficial palpable lymph nodes, subcutaneous lesions and thyroid nodules. US might also be useful to confirm the complete disappearance of superficial lesions usually assessed by clinical examination.
- The utilisation of endoscopy and laparoscopy for objective tumour evaluation has not yet been fully and widely validated. Their uses in this specific context require sophisticated

equipment and a high level of expertise that may only be available in some centres. Therefore, the utilisation of such techniques for objective tumour response should be restricted to validation purposes in specialized centres. However, such techniques can be useful in confirming complete pathological response when biopsies are obtained.

- Tumour markers alone cannot be used to assess response. If markers are initially above the upper normal limit, they must normalise for a patient to be considered in complete clinical response when all lesions have disappeared.
- Cytology and histology can be used to differentiate between PR and CR in rare cases (e.g. after treatment to differentiate between residual benign lesions and residual malignant lesions in tumour types such as germ cell tumours).

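### Entry size is set by ultrasound in section 6.1 but clinically in the summary, and nothing requires a palpable lesion although the primary endpoint is measured by callipers only

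*Protocol*

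**What the plan says.** The protocol gives the size criterion in two forms, both in current text:

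- Trial Summary, main selection criteria: "Breast tumour >2cm by clinical evaluation".
- Section 6.1, the inclusion list: "Tumour, measured on U/S, as greater than 2 cm in diameter".

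Section 7 uses tumour size (>2-5 cm, >5 cm) as a minimisation factor without saying how size is measured.

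Section 14.1 ties the primary outcome to one instrument: "Objective clinical response as measured by callipers is defined as either a partial or complete response". Partial response is a fall of at least 30% in the largest calliper dimension. For complete response, "A complete clinical response (CR) is defined as no palpable lesion from which to take calliper measurements".

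Section 9 lists among the screening assessments "Uni-dimensional tumour measurement by calipers of the greatest dimension", and Figure 1 repeats it. Neither sets a minimum.

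Appendix 4 (RECIST quick reference) says: "Only patients with measurable disease at baseline should be included in protocols where objective tumor response is the primary endpoint". It also asks for the same method at baseline and follow-up, and adds: "When the primary endpoint of the study is objective response evaluation, ultrasound (US) should not be used to measure tumour lesions".

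**The concern.** The two criteria can disagree about the same woman, and site staff confirming eligibility at randomisation need one rule.

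The difference reaches the primary endpoint because 6.1, the operative list, admits on a method that the endpoint does not use. A woman with an impalpable tumour over 2 cm on ultrasound passes 6.1. She then has no calliper value from which a 30% fall can be computed, and she fits the complete-response wording on the day she enters.

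The text gives conflicting signals on how to count her. Section 14.1 read literally makes her a complete responder. Appendix 4 treats a patient who cannot be assessed as a failure. Section 14.2 applies intention to treat. Whichever is chosen, her outcome carries no information about treatment. An analysis plan could settle the coding, but it could not supply a baseline that never existed.

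**Working it through.** **1. The passages side by side**

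| Place in protocol | Method | Threshold |
|---|---|---|
| Trial Summary | clinical evaluation | >2 cm |
| Section 6.1 | ultrasound | >2 cm |
| Section 7, minimisation | not stated | >2-5 cm, >5 cm |
| Section 9 and Figure 1, screening | callipers and ultrasound | none |
| Section 14.1, primary outcome | callipers only | none |
| Appendix 4 | conventional techniques (or spiral CT) | ≥20 mm (≥10 mm) |

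Two kinds of patient must be kept apart:

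- *Impalpable, >2 cm on ultrasound.* Eligible under 6.1, no calliper baseline, fits complete response at entry. This is the problem case.
- *Palpable, below 2 cm by callipers, >2 cm on ultrasound.* Eligible under 6.1, with a usable baseline. A 30% fall can be computed and she is not a complete responder. Section 14.1 is not at fault here.

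The methods are not interchangeable. For the letrozole arm of the neoadjuvant trial described in section 3.2.1, response was 55% clinically and 35% by ultrasound.

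**2. The plan's own sample size**

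Inputs from section 14.3: control rate 55%, 5% significance (taken as two-sided, which is not stated), 250 per arm for 13 points at 85% power, and 500 per group for 9 points at 80% power.

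With p̄ = (p₁+p₂)/2 and Φ the standard normal distribution function,

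power = Φ{ [ |p₂−p₁|√n − 1.96√(2p̄(1−p̄)) ] / √(p₁(1−p₁)+p₂(1−p₂)) }

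- 55% v 68%, n = 250 per arm: 85.0%. This agrees with the plan.
- 55% v 64%, n = 500 per group: (0.09×√500 − 1.96×0.694)/0.691 = (2.012 − 1.361)/0.691 = 0.943, so power is 82.7%. Solving for n at 80% power gives 466 per group, or 488 with continuity correction, against 500 planned.

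The stated sample size reproduces.

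**3. Illustration of dilution**

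Let f be the share of randomised women with no palpable lesion at baseline. The protocol gives no value, so f is an assumption. It is taken as equal in all arms, with 55% v 64% holding among the rest.

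- Counted as non-responders: rates 0.55(1−f) and 0.64(1−f), n = 500.
- Counted as complete responders: the same rates plus f, n = 500.
- Excluded: rates 0.55 and 0.64, n = 500(1−f).

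Example, f = 5%, non-responders: 0.5225 v 0.608, so (0.0855×√500 − 1.96×0.701)/0.698 = (1.912 − 1.374)/0.698 = 0.77, and power is 77.9%.

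| f (assumed) | Non-responders | Complete responders | Excluded |
|---|---|---|---|
| 0 | 82.7% | 82.7% | 82.7% |
| 2% | 80.8% | 81.4% | 82.0% |
| 5% | 77.9% | 79.4% | 80.8% |
| 10% | 72.9% | 75.9% | 78.6% |

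Power reaches 80% at f of about 2.9%, 4.2% and 6.8% respectively.

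**The case against.** The best defence is that the protocol plainly expects a calliper baseline. Section 9 presents its assessments as required, and a calliper measurement at screening is one of them. If Appendix 4 binds, its measurable-disease rule already speaks against entering the impalpable case. This shows intent but does not close the gap. The screening measurement is a procedure with no minimum, and Appendix 4 is a generic quick reference that section 6.1 does not cite. If it is applied, it also argues against measuring lesions by ultrasound, which is the method 6.1 relies on.

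The minimisation levels fit the ultrasound criterion exactly. A level for 2 cm or less is missing only if the factor uses callipers, which the text does not say. What remains is a minor ambiguity about method.

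A reader might infer that anyone below 2 cm by callipers lacks a usable baseline. Section 14.1 does not support that, because it sets no minimum calliper size. A reader might also take Appendix 4 to demand 20 mm by whichever method is in use, but it says conventional techniques. Nor do the documents show that power falls below 80%: that depends on an assumed share and on how these women are counted.

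It also stands that f is fixed before treatment, so randomisation spreads such women over the arms.

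**Conclusion.** The inconsistency is real and should be fixed. Two current passages set the size criterion by different methods, a third names none, and under 6.1 a woman can enter with no palpable lesion although the primary endpoint is read by callipers only. This assumes that 6.1 governs, as the operative list normally would; under the summary wording she would not be eligible.

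The consequence is confined to impalpable tumours and amounts to dilution in every arm, not bias between arms. Its size cannot be derived from the protocol: negligible at a share of 2%, and a loss of about 2 to 5 points of power at 5% and 4 to 10 points at 10%, depending on how these women are counted. Confidence is high on the contradiction and low on the power loss.

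**What to change.** - Reconcile the Trial Summary, section 6.1 and section 7 so that the size criterion and the minimisation factor use one stated method.
- Add to 6.1 that a palpable, calliper-measurable lesion must be recorded at baseline.
- Have the sponsor state, in the same reconciliation, whether a minimum calliper size also applies. The documents do not force a 2 cm calliper threshold, and imposing one would exclude women with smaller palpable lesions who can be assessed.

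The cost is a few reworded lines, plus the loss of a few women with ultrasound-only tumours and so slightly slower accrual. The change belongs before enrolment, since a missing baseline cannot be recovered once treatment has begun.
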